4.0 Study Population

4.1 Recruitment of Clinics and Practitioners Managing AF Patients

IMPACT-AF will seek participation from a wide variety of primary care providers managing AF patients within Nova Scotia. All patients with a prior or new electrocardiographically confirmed diagnosis of AF during the study period will be eligible for inclusion as part of the study.

Inclusion Criteria: Any licensed medical provider of community-based adult patients with a minimum of 15 diagnosed AF patients enrolled in the study from their practice will be eligible to participate. To avoid bias based on technological availability or proficiency, all eligible providers are required to have access to high-speed internet access in their office for the duration of this study. As well, participating providers must sign a site agreement which outline the following terms:

- Agree to participate for the duration of the study;
- Notify the research team if your practice:
 - Is located in an urban (population $\geq 10,000$) or rural (population $< 10,000$) setting; and,
 - Operates as a collaborative practice (i.e., shares in the care of patients with at least one other health care provider);
- Attend and participate in investigator meetings;
- Identify all eligible patients in your practice who meet the study inclusion criteria;
- Invite all eligible participants to join in the study (either in person or via mail outs);
- Perform informed consent discussions with eligible participants who visit your practice for routine care;
- Accept randomization into either the control or intervention group;
- Agree to store informed consent forms and completed patient questionnaires in locked filing cabinets in an access-controlled location within your practice (after faxing a copy to the study office);
- Agree to be trained on and use the web-based decision support tool, if assigned to the intervention group;
- Allow the study team access to medical records for consented study participants at baseline and follow-up;
- Facilitate the distribution of patient questionnaires (all materials supplied by the research team);

CONFIDENTIAL

- Notify the Privacy Officer at HITS-NS that the study team is to be granted access to data for all patients who consent to study inclusion and provide copies of patient signed consent forms as requested.
- Report any problems that you experience related to your participation in the study.
- Agree not to disclose or use any study related information for purposes other than the delivery of standard AF patient care and study activities.
- Agree that all information disclosed by the research team regarding the study will be considered confidential information and not disclosed, publish or disseminated to any third party other than your employees (e.g., nursing and administrative staff).

Exclusion Criteria: Providers who do not meet the above criteria will be excluded from the study.

Provider Recruitment: Doctors Nova Scotia, the medical association for Nova Scotia physicians, has been invited to identify a primary care physician to participate as a peer Champion on the project Advisory Committee. Doctors Nova Scotia and the peer champion will also be engaged and consulted to support primary care provider recruitment across Nova Scotia. Proactive provider recruitment activities are expected to include: electronic and paper-based notices (e.g., in the Doctors Nova Scotia magazine and other relevant discipline-based publications / websites), letters of invitation to participate (fax, e-mail and or hard-copy via hospital mail-boxes) sent to all primary care practices across Nova Scotia, study display booths at local medical conventions, face-to-face information sessions during community based CME events, and at specific provider meetings (e.g., family practice meetings). Recruitment will begin following confirmation of ethics approval and is anticipated to continue for 6 months, or until the desired number of practices is achieved. Promotional study materials (e.g., branded brochures, post-card, wall posters, FAQ documents, study website) will be used during the provider recruitment phase.

4.1.1 Pharmacist Participation: Consented patients will be requested to identify those pharmacies which they frequent for their medication needs. With the patient's consent, individual pharmacies will be notified by the Project Office that the patient is an IMPACT-AF study participant and invited to visit the study website for further details on the study. Pharmacy directed communications are also anticipated via regular communication channels (e.g., pharmacy websites, newsletters, etc).

4.2 Patient ID / Recruitment / Inclusion / Exclusion

Primary Care ID / Recruitment: Provider recruitment will aim to be broad to help ensure that the findings of the study can be generalized. Based upon NS billing data, the average family practice in NS is estimated to have between 20-30 adult (aged ≥ 18 years) patients with diagnosed AF. Practices will be provided with detailed written and verbal instructions on patient identification methods during the investigator orientation session entitled 'How to Create an AF Patient Registry'. EMR or billing systems can be queried (e.g., search for: ICD-9 diagnostic code 427.3 (atrial fibrillation) and or 427 (Cardiac dysrhythmias) OR ICD-10 code I48 (atrial

CONFIDENTIAL

fibrillation and flutter) billings in the last 24 months, AF diagnosis in the past history or problem list, INR monitoring / flow sheet use, use of specific medications, etc.), as well as paper-based methods utilized (e.g., tracking patients on a daily basis or using stickers / index cards) to identify potential patients with AF. Practices will be asked to create and maintain a confidential electronic registry of patient names, preferably versus a paper-based registry, that can track relevant clinical information on AF for both the practice and IMPACT-AF purposes. The expectation is for participating practices to explore their total patient population for patients with AF, not just those known to have the condition.

Other options for patient identification include: providers can request from MSI a list of those patients whom the provider has billed for an AF-related visit or INR monitoring in the last 12-24 months. Project support staff, or other peer champions, will be available after investigator orientation to support practices requiring assistance in patient identification, consenting and registry creation.

Once eligible patients are identified, a consent brochure will be mailed or handed to the patient. If the patient is seen in the provider's office, consent will be sought at the time of visit. Each patient will be assigned a study number for coding purposes; otherwise, unique identifiers for health record identification and linkage will remain with the health facility at which they were recruited and where their AF care is routinely provided. This affords a mechanism to allow follow-up on long-term care procedure and events through subsequent chart review or database linkage without having to include unique health identifiers in the IMPACT-AF study registry.

AF Clinic ID / Recruitment: Patients visiting the AF Clinic at the QEII Health Science Centre will also be asked to participate and sign a consent form. The patient's primary care provider would be notified that the patient has agreed to participate via the AF clinic site.

Inclusion Criteria:

Primary Care: All new and previously diagnosed patients ≥ 18 years of age with AF and a life expectancy > 12 months will be eligible for study enrollment. In addition, patients will need to be:

- A registered and regular patient at a primary care practice participating in the IMPACT-AF study;
- Able to read, understand and communicate in English.
- A resident of Nova Scotia.

Patients in the Intervention Arm will have the option to interact with the CDSS through the patient portal, the AF Care Partner tool. These patients will therefore need access to the Internet and be willing to input information and receive feedback and reminders from the AF Care Partner tool over the duration of the study. Patients can revoke their AF Care Partner tool participation if desired.

CONFIDENTIAL

All AF Clinic (QEII HSC) patients will be invited to participate in the IMPACT-AF study by signing an informed consent form.

Exclusion Criteria: Patients with a terminal illness (expected death within 12-months) and those having cognitive impairment or who are unable to communicate in English will be considered ineligible for participation. Also ineligible for inclusion are AF patients whose care is being significantly overseen by a specialist as well as those who are patients of the hospital-based AF clinic at the QEII Health Sciences Centre.

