3.0 STUDY DESIGN

3.1 Description

The proposed project falls into the scope of what has been termed a pragmatic or practical clinical trial [109-111]. This means that the hypothesis and study design have been developed specifically to answer questions faced by policy makers as they seek to develop new and effective population health management approaches. The first goal is to develop a CDSS that has undergone preliminary assessment of its clinical usefulness by knowledge opinion leaders as well as practical field-testing of its utility and dependability in practice settings. Following this, a rigorous analytical assessment of efficacy will be undertaken.

Specifically, IMPACT-AF will include a prospective, randomized, unblinded cluster design clinical trial, proposed to take place within Nova Scotia over the time period of 2014-2018, that will investigate whether a Clinical Decision Support System (CDSS) improves the clinical outcomes of patients with AF. Primary care providers (n=200) will be randomized to usual care versus use of the CDSS in a 1:1 fashion, at the level of the clinic practice. In order to facilitate the study, primary care providers will be required to have high speed internet access. The study will follow patients over a minimum of 12 months after enrolment.

Patients Included in the Analysis:

1. Age \geq 18 years
2. Electrocardiographically confirmed atrial fibrillation or documentation of past diagnosis or management of AF in the patient's medical record
3. Able to provide informed consent in English
4. Resident of Nova Scotia

Exclusion Criteria:

1. Patients unable to provide informed consent
2. Patients who have a terminal illness and are not expected to be alive at the end of follow up.

3.2 Study Flow:

See Figure 5 for a Summary of Study Flow.

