3.7.3 Data Collection

Once informed consent has been obtained by the patient's PCP, a process to record retrospective baseline and ongoing clinical data prospectively will be implemented. Patients will be also requested to complete a patient case report form and quality of life questionnaire (either paper-based or electronic format) to gather relevant demographic and socioeconomic data.

Acknowledging the age profile of AF patients in NS, it is anticipated that a proportion of

CONFIDENTIAL

participants will chose not to complete online surveys or interact with the web-based tool. Completion of the web-based survey tools and / or interacting with the web-based tool, the AF Care Partner, is not mandatory for participation; all survey tools will be available to participants in a paper-based format.

In both study arms, baseline clinical data will be captured from the patient's chart by a data abstractor via on-site visit(s). Abstractors will utilize a laptop computer or tablet to record and transmit study data to secure and password protected servers located behind a firewall at Health Information Technology Services Nova Scotia (HITS-NS). This process will be repeated at 12 months for follow-up data collection in both study arms. Follow-up data for the intervention arm will also be captured through examination of data gathered during use of the CDSS.

The majority of patients at the start of the study are expected to have a past diagnosis of AF. As the study progresses, newly diagnosed patients are anticipated to be enrolled.

Review of PCP records will be done at 12 months to ensure completeness of outcome events. Clinical event / outcomes data will also be captured via review of hospitalization records for consented patients. Patients visiting the AF clinic in Halifax will be consented and data captured during their clinic visit. See Section 4.2 for further details.

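### A sentence under the inclusion criteria in Protocol 4.2 can be read as requiring internet access and portal use of intervention-arm patients only, against 3.7.3; it should be limited to patients who choose the portal

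*Protocol*

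**What the plan says.** Protocol 4.2 gives the primary care inclusion criteria as an opening sentence (adults with AF and a life expectancy above 12 months) and three bullets: regular patient of a participating practice, English, Nova Scotia residence. A separate paragraph follows, still under the inclusion heading. It makes three statements in order:

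- The AF Care Partner portal is offered to intervention-arm patients as an option.
- The next sentence reads "These patients will therefore need access to the Internet and be willing to input information and receive feedback and reminders", and it extends this requirement to the whole study period.
- The paragraph then allows withdrawal from the tool: "Patients can revoke their AF Care Partner tool participation if desired".

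Protocol 3.7.3 refers to the age profile of AF patients in the province and anticipates that a proportion of "participants will chose not to complete online surveys or interact with the web-based tool". It then states: "Completion of the web-based survey tools and / or interacting with the web-based tool, the AF Care Partner, is not mandatory for participation". Paper versions of all the surveys are to be offered.

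The patient criteria in Protocol 3.1 contain no internet condition, and the exclusions in 4.2 do not list lack of internet. The internet requirement in 3.1 and 4.1 is on providers in both arms. Section 4.1 gives its purpose as avoiding bias from technology availability or proficiency.

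**The concern.** The subject of the middle sentence in 4.2 is loose. Its only grammatical antecedent is all patients in the intervention arm, not those who take up the option. It sits under the inclusion heading, speaks of need, and runs for the whole study. A practice that reads 4.2 alone can take it as a condition of entry that has no counterpart in the control arm.

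The design makes such a reading matter. The trial is unblinded (3.1), practices learn their arm when they are recruited (3.7.1), and the patient's own provider obtains consent (3.7.3). The person applying 4.2 therefore knows the allocation. Section 3.6 regards recruitment bias as limited because every patient in a practice is to be included, and a condition applied in one arm would remove that protection. Intention-to-treat analysis does not help, because it covers only patients who were enrolled.

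The planned analysis would not reliably repair the damage. The primary GEE model adjusts for urban or rural practice only (Protocol 3.9; SAP, Primary Outcome Analysis). Protocol 3.9 promises a sensitivity analysis for baseline imbalance but names no covariates, and the SAP's sensitivity analyses do not include it. SAP Table 2 lists age but not internet access or income.

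**Working it through.** **Step 1: is there an entry condition?**

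| Place | What it implies about internet or portal use |
|---|---|
| 4.2, sentence before | Portal is an option for intervention patients |
| 4.2, sentence at issue | Intervention patients need internet and willingness, for the whole study |
| 4.2, sentence after | Portal participation can be revoked |
| 4.2, bullets and exclusions | No internet condition |
| 3.1, inclusion and exclusion lists | No internet condition on patients |
| 3.7.3 | Portal use not required for participation; surveys on paper |

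One row of six supports an entry condition. The others support a requirement that attaches to an optional tool. An option cannot by itself create a need for every patient in the arm, so the paragraph makes sense only if the middle sentence is confined to portal users. It does not say so.

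**Step 2: the planned effect, as the yardstick.** Protocol 3.8 assumes 50% versus 40%, two-sided alpha 0.05, power 80%, ICC 0.05 and 9 patients per cluster.

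- Unadjusted total: 2 × (1.96 + 0.84)² × (0.5×0.5 + 0.4×0.6) / 0.10² = 768.32.
- Variance inflation: 1 + (9 − 1) × 0.05 = 1.4.
- Adjusted total: 768.32 × 1.4 = 1075.65, which matches the plan's 1075.

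No figure in the plan is in dispute. The yardstick is the 10-point difference.

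**Step 3: what one-arm screening could do, under assumptions.** The documents give neither the share of eligible patients who are offline (f) nor their event risk relative to online patients (r). Both are assumed here: f from 10% to 40%, r from 1.0 to 1.4. Control risk is 50% and there is no true effect. Let s be the share of offline patients screened out of the intervention arm.

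- Online risk = 0.5 / (1 − f + f·r); offline risk = r × online risk.
- Offline share left in the intervention arm: w = f(1 − s) / (1 − f·s).
- Spurious difference = 0.5 − [online risk × (1 − w) + offline risk × w].

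Example: f = 0.3, r = 1.2, s = 1 gives an online risk of 0.5/1.06 = 0.4717 and w = 0, so the difference is 2.8 points.

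| Offline share | r = 1.2, all screened out | r = 1.2, half | r = 1.4, all | r = 1.4, half |
|---|---|---|---|---|
| 10% | 1.0 | 0.5 | 1.9 | 0.9 |
| 20% | 1.9 | 0.9 | 3.7 | 1.6 |
| 30% | 2.8 | 1.2 | 5.4 | 2.2 |
| 40% | 3.7 | 1.4 | 6.9 | 2.6 |

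Entries are percentage points in favour of the intervention. At r = 1.0 every entry is 0. At s = 0, which is what 3.7.3 directs, every entry is also 0.

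**Step 4: numbers enrolled.** If screened-out patients were not replaced, an offline share of 10–40% would take the intervention arm from 537 to 483–322. Power for 50% versus 40% would go from 79.6% to 78.1–71.0%, allowing for the smaller intervention clusters. This is secondary to the bias.

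**The case against.** The strongest answer is that the protocol, read as a whole, already settles the matter. The sentence lies outside the bulleted criteria and follows directly from one that offers the portal as an option. Section 3.7.3 is an express rule on participation, whereas the contrary reading rests on placement. Section 4.1 has providers identify and invite all eligible patients. Internet access, age, income and education are among the data collected (3.7.3), so differential selection could be seen and partly adjusted for. All of this stands, and it makes the benign reading the probable intention.

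The objection does not remove the loose wording. A site has to combine 4.2 with 3.7.3 to reach the intended rule, and eligibility text should not depend on that. Data that could reveal selection are also of limited use when the SAP does not plan to tabulate internet access.

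Three stronger inferences are tempting, and the documents do not support them.

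- *The protocol sets an internet criterion in one arm, so sites would screen out older offline patients.* The text supports only that a site could do so if it took the sentence literally. Section 3.7.3 links non-use of web tools to age, but it speaks of a proportion of participants and gives no figure.
- *The result is biased by several points.* The offline share, the risk gap and the extent of literal application are all assumed.
- *Revoking the tool ends trial participation.* Section 4.2 speaks of revoking the tool, 3.7.3 separates tool use from participation, follow-up is by record review in both arms, and the analysis is by intention to treat. The only gap is that 4.2 does not say so.

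**Conclusion.** The point holds as contradictory eligibility wording with a possible one-arm consequence. It is not a demonstrated selection bias or a firm arm-specific criterion. The sentence in 4.2, taken literally, conflicts with its neighbours and with 3.7.3. Because allocation is known before consent, a literal application would act in the intervention arm only and would undercut the reasoning in 3.6.

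The size is unknown. It is zero if sites follow 3.7.3, and zero if offline patients carry the same risk as online patients. The range of 0 to 6.9 points assumes that every offline patient is screened out of one arm and none out of the other; with half screened out it is 0 to 2.6. These figures show only why the ambiguity is worth removing when the planned effect is 10 points. They do not estimate what happened. The change should be made because it is nearly free and the planned analyses would not reliably correct the problem if it arose.

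**What to change.** 1. Move the sentence out of the inclusion criteria in 4.2 and replace it with: *Intervention patients who choose to use AF Care Partner need internet access; internet access or willingness to use the tool is not a condition of enrolment in either arm.*
2. Add: *A patient who declines or revokes the tool remains enrolled, is followed to 12 months and is analysed in the assigned arm.*
3. Put the same wording in the site instructions.
4. Add internet access to SAP Table 2, next to age, and report both by arm. A lower offline share among enrolled intervention patients would be a warning sign. If sites kept a screening log, report by arm the numbers eligible, approached and consented.

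The cost is two sentences, a site notice and one table row from data already collected. The downside is lower recorded portal uptake in the intervention arm. If enrolment has closed, items 1 and 3 can no longer change recruitment, and item 4 is the part that still has value.

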4.3 Ethical Considerations

IMPACT-AF is a non-interventional study. There is no assignment of a patient to a particular therapeutic strategy; instead, the treatment decision falls within the boundaries of acceptable current practice and treatment options remain the decision of the primary care provider.

Ethics approval will be solicited through the Nova Scotia Multisite Research Ethics Board. Providers will be required to sign a site agreement. Patient consent will also be sought from all participants at the beginning of their involvement in the study. Consent forms will be standardized to adhere to local ethics criteria and good clinical practices, with reference to all planned data capture including clinical, demographic, socioeconomic, economic and health care utilization information. The consent process will be as previously outlined.

Provider and patient confidentiality will be maintained via encryption of all electronic study data. Only Canadian servers will be utilized to host the study registry and clinical decision support system with the servers housed at the Nova Scotia government's provincial data center. The CDSS, AF Care Partner and participant data will be stored on firewall and password protected servers located at HITS-NS. A unique Study ID is created for each patient following enrollment in the study. A participant registry stores the name and corresponding Study ID for each participant. All study data collected will be stored by Study ID and names will be removed and kept separate from the participant registry. The intervention tool (CDSS) will also be stored on servers at HITS-NS; when a Primary Care Provider and / or patient interacts with the intervention tool, all data is immediately sent and stored on these servers.

All study researchers, staff, Site Investigators and participants will access the servers through a secure login requiring unique usernames and passwords. Individuals will be permitted access to only the information required for their role in the study.

Hard copy study forms maintained at the Study Coordinating Centre (e.g., any patient data or AF clinic consent forms, etc) will be maintained in a secured locked cabinet in a secure location on the QEII HSC property.

